BACKGROUND	
Renal denervation (RDN) is a recent procedure that can be used to control BP (blood pressure) in hypertensive patients. Numerous publications from randomised trials have demonstrated the efficacy of RDN in this indication (1-14). The latest guidelines now include RDN as an effective technique for use in hypertension. Since the beginning of 2023, RDN using Medtronic's Spiral radiofrequency system has benefited from transitional authorisation for reimbursement by the French health insurance system. An application for reimbursement is underway for the ultrasound system.
 
We aim to compile an exhaustive prospective register of all procedures carried out in France over the next few years, regardless of the type of catheter used or the context in which the procedure was carried out (transitional reimbursement, industrial register, randomised trial). Our aim is to assess the efficacy and safety of the procedure within the French healthcare system, the characteristics of patients benefiting from the procedure, the centres performing renal denervation, and the care pathways used, and to be able to present all this data, independently of the industry, to the healthcare authorities when it comes time to reassess the value of this procedure and its indications.

PRIMARY OBJECTIVE	 Diagnostics  Prevention and treatment  Patient management  Patient safety  Organization of healthcare facilities  Public health policies  Understanding diseases  Other: To describe changes in SBP evaluated in Home Blood Pressure Measurement (HBPM) in hypertensive patients between before and 1 year after treatment with RDN.
PRIMARY ENDPOINT	Change in SBP measured by HBPM before and after RDN (1 year).
SECONDARY OBJECTIVES	SECONDARY OBJECTIVES: - To evaluate changes in office systolic blood pressure, the combination of SBP measured in HBPM and day ABPM and 24-hour SBP before and 3 months, 6 months, 1 year, after DNR. - Evaluate the evolution at 3 months, 6 months, 1 year, of the drug burden in antihypertensive treatment (DDD), the percentage of patients having reached the blood pressure target and the win ratio. - Evaluate the development of renal artery stenosis before and 6 months, 1 year, after DNR. - Evaluate the evolution of creatinine levels before and 6 months, 1 year, after DNR. - Evaluate the occurrence of other complications related to hypertension or to the procedure itself. - Comparison of responders and non-responders to the procedure (24h ABPM systolic blood pressure decrease of 5 mmHg or more and/or the diminution of the medical burden by at least one therapeutic class without SBP increase compared to baseline). - Evaluate the performance of known predictors of response to renal denervation in our population. - Describe the type of center performing the procedure, the context in which DNR is performed, patient characteristics and care pathways.
METHODOLOGY	Research that does not involve the human person, as it involves the prospective, retrospective, descriptive and comparative use of multicentric data from routine care.
TYPE OF DATA COLLECTED	The data collected are detailed below: 
 • Administrative data : - centre number followed by a hyphen (-) then the patient's number - collection of the patient's non-objection to participate in the FRiEND register - date of inclusion, date of procedure

	
 - type of centre carrying out the procedure (hospital, university hospital, clinic, ESPIC, other) - setting in which the procedure was carried out (day hospitalisation, week hospitalisation, conventional hospitalisation) 
• Personal data :
 
 - Patient's initials, date of birth (in MM/YYYY format). - Gender (male, female, not gendered, refuses to answer), height, weight, 
• Biological data :
 
 - Biological work-up with measurement of the following parameters: Plasma ionogram (Na, K), blood count and platelet count (NFP), proteinuria, fasting glycaemia, total cholesterol, LDL cholesterol, HDL cholesterol, triglycerides, creatininaemia, estimated glomerular filtration rate (eDFG) (according to the Modification of Diet in Renal Disease (MDRD) method), uricaemia, microalbuminuria or urinary albumin/creatinine (assessment of target organ damage). 
• Clinical data :
 
 - Systolic blood pressure (SBP), diastolic blood pressure (DBP), heart rate (HR): three measurements will be taken with a validated oscillometric electronic device measured according to international recommendations (2023ESH-ESC) - risk factors (dyslipidaemia, type 2 diabetes, hypertension, smoking) - cardiovascular (CV) history of more than 6 months (myocardial infarction, coronary insufficiency, stroke) - non-CV history (cancer, asthma or respiratory insufficiency, musculoskeletal disability) - ABPM measurement (SBP and DBP for 24 hours, during the day and at night) - self-measurement of BP (according to the rule of 3 : average of 3 measurements in the morning and 3 in the evening, 3 consecutive days). - current treatments (anti-hypertensive, lipid-lowering, anti-diabetic, anti-platelet). - Therapeutic adherence assessment 
• Imaging data :
 
 - results of CT scan of renal arteries: number of renal arteries, diameter of renal arteries, assessment of possible renal artery stenosis (in %) - Renal artery echodoppler (if feasible): assessment of possible renal artery stenosis (in %), renal artery blood flow velocity.
--	---

	
● Procedure:
- Indication validated by a Centre of Excellence or Blood Pressure Clinic (yes/no)- Complete secondary hypertension work-up (yes/no)- In particular: plasma renin/aldosterone assay? Methoxylated catecholamine derivatives? renal artery imaging?- Precise indication of the procedure- context of treatment (temporary reimbursement of SIMPLICITY catheters, registry, randomised study)- specialities of the doctor(s) performing the procedure,- details of the procedure: under general anaesthetic/analgesia, approach,- Antithrombotics and anti-platelet aggregants before, during and after the procedure- number of ablation/sonication points performed- volume of contrast medium used, X-ray dosimetry- closure system for the approach port- complications, if any● Follow-up data :
- Date and type of follow-up- Progress of treatment- clinical BP measurements, MAPA and self-measurements performed- Changes in biological markers- Changes in imaging of the renal arteries- Complications, if any 
This might include retrospective data for patients treated with RDN in the past, if investigator believe that the missing data are absent or scarce. As we will collect only data coming from a routine care already widely used in France for these patients, this should correspond to most of the patients already treated with RDN. Patients included retrospectively and prospectively will be compared to ensure that there are no selection biaises in the retrospective cohort.
 
Use one or more of the following sensitive variables :
 
 Country and department of residence of the person studied (NB: the collection of the commune of residence (zip code and/or name) is not permitted) Pays et département de résidence de la personne étudiée (NB : le recueil de la commune de résidence (code postal et/ou nom) n'est pas autorisé)
 
 Year and month of birth

--	---

	 Date of care (DDMMYYYY)  Date of death (DDMMYYYY)  City of death  None
ORIGIN OF DATA	 Medical record  Survey / Cohort / Register not including SNDS data  Other data
	 Data from the investigator's department only (coordinating and associated centers)  Data from several departments of the CHU Grenoble Alpes or from a department other than that of the investigator (if the investigator is at no time involved in the care of the persons targeted by the research).
DATA COLLECTION SCHEDULE	
Prospective and retrospective research :
 
 - 3-year register (start of collection april 2025 - end of inclusions april 2027, follow-up : 1 year) 
For retrospective patients, data collection will be done from clinical database from january 2010. A 4-week delay must be observed between the sending of information letters and the start of data collection.
 
 - End of follow-up: april 2028. - Annual analysis of data from patients who have undergone RDN and follow-up at 1 month, 6 months, 1 year after the procedure.
DATA COLLECTION	
Collection :
 
The data collected will be those from routine follow-up at 1 month, 6 months, 1 year of all patients benefiting from a RDN procedure and included in the registry. After the procedure, the investigator in each participating centre will manage the follow up of the patient. As the study is purely observational, it does not require any specific follow-up visits, but includes the collection of data obtained during routine follow-up visits. The registry does, however, include data collection at fixed times after procedure. The data reported in the Redcap file will be the data available closest to the theoretical day of collection.
 
Patients who have been lost to follow-up should be investigated through the referring doctors to RDN and/or by family members or any other person whose name appears on the patient liaison form. In the absence of any information, a search for the patient's possible death will be carried out by consulting the https://deces.matchid.io/searchqui website, including the INSEE source for deaths (the search will be carried out by birth name).
 
In case of the patient's death, the medical record is first checked to ensure that the patient has "no objection" to the use of his or her health data for research purposes.
 
Clinical data collection will be based on the source documents.

	
Codage :
 
The data will be pseudonymised by coding: patients will be identified as follows: centre number followed by a hyphen (-) then the patient number coded number specific to the research indicating the order of inclusion of subjects (ex. 01-001). The list of correspondences between the patient code and his identity will be kept in each participating center, in the service server, by the investigator on an Excel file.

DATA STORAGE PERIOD	
Personal data relating to persons taking part in research, and processed for this purpose, may be kept in the information systems of the controller, the participating centre or the healthcare professional involved in the research for a maximum of 2 years after the last publication of the results of the research or, if there is no publication, until the final report of the research is signed.
 
The personal data of the professionals involved in the research may not be kept for more than fifteen years after the end of the last research project in which they participated.
 
It is then archived on paper or electronically for a period of time in accordance with the regulations in force. The data must then be deleted.

DESCRIPTION OF STATISTICAL ANALYSIS OF DATA	
NUMBER OF SUBJECTS TO BE INCLUDED
 
The number of subjects included will correspond to the number of patients undergoing renal denervation for hypertension at the Grenoble University Hospital and in the various French centres participating in the study during the study period (the estimation is currently 100 per year).
 
DATA ANALYSIS
 
The database will be stored in accordance with the signed investigator commitment, on a secure database certified to keep health data, and linked to the REDCAP system supporting the eCRF. The analyses will be carried out at the University Cardiology Clinic of the Grenoble University Hospital by [name] and [name] with the help of the SFHTA, using SPSS version 21 (SPSS Corp, Somers, NY) and STATA® 14.1 (Stata Corporation, College Station, TX).

	
Statistical analysis: Absolute values, percentages and means (SD) will be calculated to describe the population.
 
The differences between the variables before and after the RDN will be tested using either a paired t-test for normally distributed data or a Wilcoxon test, and a paired Chi2 or a Fisher test. For univariate analysis of variables between the RDN responder groups (5 mmHg reduction in 24h SBP) and non-responders, we will use the t-student analysis of variance test or non-parametric tests for continuous variables, and chi2 or Fisher tests for categorical variables. A multivariate analysis will also be performed.

PEOPLE INCLUDED IN THE RESEARCH	
Number of subjects: Estimation of 100 per year (might be less in the first year, then more as RDN implementation in France increase)
 
Inclusion criteria: Adult (> 18 years old) hypertensive patients treated with RDN in France whatever the catheter and the indication. This might include retrospective data for patient already treated with RDN in the past.

	
Non-inclusion criteria: RDN not proposed to the patient, patient opposing the collection and use of his/her data for research purposes.
 
Information and traceability procedures for non-objection/opposition :
 
Patients will be fully and fairly informed, in comprehensible terms, of the objectives of the study and the nature of the information collected, and of their right to object at any time to the use of the data collected. They will be given an information letter and the non opposition will be written down in the medical records of the patient. If the subject objects to their personal health data being processed for research purposes, this objection will be recorded in their medical file. This right of objection may be exercised at any time by any means with either the person responsible for the research or the establishment holding the data, which undertake to respond to the request within a maximum of 2 months.
 
Retrospective patients will be informed by post. On receipt of this letter, the patient will have 4 weeks to object.

ETHICS	NA
WHY THE STUDY IS IN THE PUBLIC INTEREST	The legal basis for this data processing is Article 6 of the General Data Protection Regulation (GDPR), namely the performance of a mission of public interest assigned to the data controller and the legitimate interests pursued by it. In addition, under Article 9 of the GDPR the data controller may exceptionally process special categories of data, including health data notably for scientific research purposes.
EXPECTED BENEFITS	
To objectively evaluate RDN performance, patients and center profiles and care pathway in the various French centres participating to the registry, and to investigate whether there are any predictive factors (on the basis of the initial clinical and biological work-up) for the outcome in terms of lowering blood pressure, in order to better target patients who could benefit from this type of procedure in the future.
 
Provide informed, independent data to the health authorities to support reimbursement decisions and the choice of indications.

Study schedule

Visits	During hospitalization for RDN	1 month after RDN	6 months after RDN	12 months after RDN
Patient information	X			
RDN indication verification	X			
Blood sample	X			
Imaging examinations	X			
Medical history collection	X			
Clinical examination	X	X	X	X
Ongoing therapy collection	X	X	X	X
Adverses events recording	X	X	X	X
Blood Pressure and heart rate recording	X	X	X	X
Blood sample				
Ionogram (Na, K), glucose level, creatininemia (DFG MDRD), uricemia	X	X	X	X
Total Cholestérol, HDL, LDL triglycerides, NFP				X
Microalbuminuria, proteinuria				X
Clinical examinations				
Home Blood Pressure Measurement		X	X	X
Ambulatory Blood Pressure Measurement				X
Renal Arteries ultrasound				X
Renal arteries angioCT				X

Bibliographie :

1. Adherence to Antihypertensive Treatment and the Blood Pressure-Lowering Effects of Renal Denervation in the Renal Denervation for Hypertension (DENERHTN) Trial. Azizi M, Pereira H, Hamidouche I, Gosse P, Monge M, Bobrie G, Delsart P, Mounier-Véhier C, Courand PY, Lantelme P, Denolle T, Dourmap-Collas C, Girerd X, Michel Halimi J,

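### The primary endpoint needs a home blood pressure from before renal denervation, but the study schedule and the collection rule give that reading no time point

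*Protocol*

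**What the plan says.** **What needs a baseline.** The PRIMARY ENDPOINT is "Change in SBP measured by HBPM before and after RDN (1 year". The section on statistical analysis compares values before and after the procedure with paired tests. The SECONDARY OBJECTIVES define response partly by a fall of at least 5 mmHg in 24-hour ambulatory systolic pressure.

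**What is listed as data.** Under TYPE OF DATA COLLECTED, the clinical data include 24-hour ambulatory pressure and self-measured pressure, the latter with its measuring rule (three morning and three evening readings over three days). These items stand apart from the follow-up block, which lists ambulatory and self-measured pressure again.

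**What is scheduled.** The Study schedule has four columns: "During hospitalization for RDN", then 1, 6 and 12 months. The row "Home Blood Pressure Measurement" is marked at 1, 6 and 12 months. The row "Ambulatory Blood Pressure Measurement" is marked at 12 months only.

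**How a value is chosen.** DATA COLLECTION describes the data as coming from routine follow-up at 1 month, 6 months and 1 year. It then says: "The registry does, however, include data collection at fixed times after procedure". The next sentence is the selection rule: "The data reported in the Redcap file will be the data available closest to the theoretical day of collection".

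**The concern.** The registry describes no control group, so the reading from before the procedure is the only comparator for the primary result. A centre working from the schedule and the DATA COLLECTION section alone would not be prompted to enter it. A later analysis plan cannot recover a value that was never entered, nor choose a different one if only one was.

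The choice of reading can also shift the result. A reading kept because it prompted referral would tend to be high and would enlarge the apparent fall. A reading from before a change of drugs would mix the effect of that change with the effect of the procedure. Patients treated in the past are the most exposed, since their data may be drawn from records reaching back to January 2010 and nothing says which earlier reading is to be used. The results are meant to inform health authorities, and the protocol plans to compare retrospective with prospective patients. Baselines chosen in different ways would weaken both uses.

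**Working it through.** No sample-size or effect figure bears on this point, so the check sets the sections side by side.

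**Step 1: what the endpoint requires.** Change = home systolic pressure at 1 year minus home systolic pressure before the procedure. Both terms are needed for each patient in a paired analysis. The same holds for the 24-hour ambulatory fall.

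**Step 2: what the schedule marks.**

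| Row | Hospitalisation | 1 month | 6 months | 12 months |
|---|---|---|---|---|
| Home measurement | – | X | X | X |
| Ambulatory measurement | – | – | – | X |
| Blood pressure and heart rate | X | X | X | X |
| Clinical examination | X | X | X | X |
| Ionogram, glucose, creatinine, uric acid | X | X | X | X |

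Home measurement has 0 of 1 marks outside follow-up and 3 of 3 within it. Ambulatory measurement has 0 of 1 and 1 of 3.

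**Step 3: could another row stand in?** The nearest candidate is "Blood Pressure and heart rate recording". It is marked at all four times. If it included ambulatory measurement, it would call for that at 1 and 6 months, where the ambulatory row is blank. If it included home measurement, the home row would be redundant. The data list also has a separate item for pressure and heart rate from three oscillometric measurements, which fits this row. The row "Ionogram (Na, K), glucose level, creatininemia (DFG MDRD), uricemia" shows that a detailed row can carry a hospitalisation mark. A stand-in is therefore unlikely, though not excluded.

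**Step 4: could the hospital stay be the baseline day?** The data list allows the stay to be a day hospitalisation, while home measurement runs over three consecutive days. A home baseline would then have to come from before the stay, and the schedule has no column for that period.

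**Step 5: does the selection rule reach baseline?** The rule takes the value closest to a theoretical day. The days given in DATA COLLECTION are 1, 6 and 12 months after the procedure. Theoretical days defined before the procedure: 0.

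**Step 6: is the reading dated?** The data list names dates of inclusion, procedure and follow-up. It names none specifically for the home or ambulatory reading before the procedure, although full dates of care are declared in general.

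**The case against.** Several counter-arguments have weight.

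- **The data list already covers baseline.** It names ambulatory and self-measured pressure apart from the follow-up block. This stands. A reader might infer from the schedule that baseline readings are never collected, and the document does not support that. The fault is that they are implied in one place and given no time point in the others.
- **A blank cell proves little.** Six of the seven detailed rows are blank at hospitalisation. For four of them (lipids and blood count, urine protein, renal ultrasound, renal CT) a general row marked only at hospitalisation may stand in. Home and ambulatory measurement have no such row, but they sit under a sub-heading that resembles the general clinical examination row. This contrast is a matter of interpretation, and the point does not rest on it.
- **The selection rule does not itself say post-procedure.** True: that limit comes from the sentence before it. One could read the rule as the nearest reading before the procedure date. But no baseline day is defined, so another centre could read it differently.
- **A baseline window belongs in the SAP or eCRF.** This stands for the maximum age of the reading. The follow-up rule has no maximum distance either, though it does have target days. It does not excuse a schedule that omits half of the primary endpoint.
- **Retrospective patients are screened.** They may enter only if the investigator judges that little is missing. This bears on absent baselines, but not on which of several readings is used.

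A reader might also treat the record span as the size of the problem: January 2010 to April 2025 is 15 × 12 + 3 = 183 months. That is how far back the records reach, not the gap between any reading and its procedure.

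**Conclusion.** The point holds as a conflict between sections. The endpoint, the paired tests and the responder definition need home and ambulatory readings from before the procedure, while the schedule and the collection rule provide only for readings after it. It should be fixed, because the reading is the only comparator and the choice has to be settled when data are entered. It does not show that baselines are missing or that the result is biased. Neither the number of patients affected nor the effect on the mean change can be derived from the document. The conclusion assumes that the schedule's blank cells are as printed. Neighbouring rows keep their hospitalisation marks and the text of DATA COLLECTION agrees with the table, so a reading fault is unlikely.

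**What to change.** Reconcile the objectives and endpoint, TYPE OF DATA COLLECTED, DATA COLLECTION and the Study schedule:

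1. Add a pre-procedure column to the schedule that marks home and ambulatory measurement as dated values from the routine work-up.
2. Extend the selection rule so that baseline is the last available reading before the procedure date, with its date recorded. Apply it alike to prospective and retrospective patients.
3. Count patients without such a reading as missing baseline.

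The maximum age of the reading may be set in the SAP or eCRF.

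The cost is one column and one or two sentences. No visit is added, since the values come from routine records, and recording their dates fits the dates of care already declared. The downside is that some patients, mainly retrospective ones, will show a missing baseline.

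### Cardiovascular history is collected only if older than 6 months, although patients with a more recent event are eligible, so recent infarctions and strokes have no named baseline field

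*Protocol*

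**What the plan says.** Under TYPE OF DATA COLLECTED, clinical data, the protocol lists "cardiovascular (CV) history of more than 6 months (myocardial infarction, coronary insufficiency, stroke". The item that follows, "non-CV history (cancer, asthma or respiratory insufficiency, musculoskeletal disability", has no time limit.

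Under PEOPLE INCLUDED IN THE RESEARCH, the inclusion criterion is "Adult (> 18 years old) hypertensive patients treated with RDN in France whatever the catheter and the indication", and past patients may be added retrospectively. The non-inclusion criteria are "RDN not proposed to the patient, patient opposing the collection and use of his/her data for research purposes". The BACKGROUND states the coverage aim: "We aim to compile an exhaustive prospective register of all procedures carried out in France over the next few years".

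The Study schedule has a row "Medical history collection", marked at the RDN hospitalisation, with no time window and no list of contents.

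Two uses of baseline history follow from the stated aims. SECONDARY OBJECTIVES includes a description of patient characteristics and a comparison of responders with non-responders. EXPECTED BENEFITS says the registry will investigate "whether there are any predictive factors (on the basis of the initial clinical and biological work-up".

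**The concern.** A 6-month limit on cardiovascular history would fit a study that excludes recent events, because the limit would then remove nothing from the enrolled population. This registry has no such exclusion and sets out to cover all procedures. The limit therefore removes information on patients whom the registry enrols, and no reason is given for it.

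Three things are at stake, all secondary. The description of treated patients, which is meant for the health authorities, may understate cardiovascular disease, and the missing part would be the most recent disease. A history variable that leaves out recent events is a flawed covariate in any predictor or responder analysis that uses it. Complications related to hypertension after RDN are harder to interpret if an event shortly before RDN is not in the dataset.

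An analysis plan cannot repair this, because it cannot analyse an event that was never entered.

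**Working it through.** The check is mainly textual. The protocol has no figure on this point to reproduce.

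**1. Does eligibility make the limit harmless?** No. The inclusion criterion requires adulthood, hypertension and treatment with RDN, whatever the catheter or indication. The two non-inclusion grounds are that RDN was not offered and that the patient objects to data use. A patient with a stroke 3 months before RDN meets the first and neither of the others.

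**2. Does another listed item record the event?** Taking the rest of the data list in turn:
- Risk factors: dyslipidaemia, type 2 diabetes, hypertension, smoking. No events.
- Non-cardiovascular history: excludes cardiovascular events by definition.
- Current treatments and peri-procedural antithrombotics: indirect markers, which identify neither an event nor its date.
- Complications: listed under the procedure and under follow-up, not at baseline.
- The schedule row on medical history: says when history is taken, not what it contains. The content is set by the data list, where the limit stands.

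So no named baseline field covers an infarction or stroke of the last 6 months.

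**3. From which date do the 6 months run?** The protocol does not say. Both an inclusion date and a procedure date are collected. For prospective patients this may matter little. Retrospective data go back to January 2010, so inclusion can fall years after RDN. If the 6 months were counted back from inclusion, a stroke that happened after RDN but more than 6 months before inclusion would qualify as history.

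**4. How many patients could be affected?** The protocol gives no frequency of recent events, so this is illustration only.
- Prospective patients: about 100 per year (DESCRIPTION OF STATISTICAL ANALYSIS OF DATA) × 2 years of inclusions, April 2025 to April 2027 (DATA COLLECTION SCHEDULE) = about 200. The 100 is an estimate, not a calculated sample size, and retrospective patients come on top.
- Assumed share with an event in the last 6 months: 1% to 5%. 0.01 × 200 = 2 patients; 0.05 × 200 = 10 patients.
- Worst case, in which each of these is the patient's only event and is entered as negative: recorded prevalence of cardiovascular history falls by 2/200 = 1 to 10/200 = 5 percentage points.
- If, as a further assumption, 40 of 200 (20%) truly have a history, the recorded figure would be (40 − 2)/200 = 19% to (40 − 10)/200 = 15%, and 2/40 = 5% to 10/40 = 25% of true positives would be missed.
- Best case: centres enter recent events despite the wording, and nothing is lost.

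**The case against.** The strongest reply is that the protocol does not show how recent events will be entered. A reader might infer that they are coded as no history. The documents do not support that as a fact: there is no coding rule, and the eCRF is not shown. A recent event could be entered as negative, left blank, noted under the general medical history row, or entered in the item anyway. This stands, and it limits the claim to events that may be lost or misclassified. It does not remove the defect, because the only item that names these conditions excludes the recent ones.

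A reader might also infer that associations with cardiovascular history will be biased toward the null. That is the usual result of non-differential misclassification, but it is not assured here. The misclassification depends on how recent the event was, and if recently ill patients respond differently to RDN, the direction could vary. The protocol also refers to known predictors of response without naming cardiovascular history among them.

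A patient who has an older event as well as a recent one is still recorded as positive. Only patients whose sole event is recent can be misclassified as having no history, which reduces the numbers further.

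Finally, the event remains in the medical record, which is the declared source of data, so it could be recovered later. That is true, but it would mean returning to the records in every centre for something that can be collected once.

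**Conclusion.** The point holds in a limited form. The data list omits cardiovascular events of the last 6 months, the eligibility criteria admit patients who have had them, and no other detailed item names them. Followed as written, the plan gives an incomplete baseline descriptor for a stated secondary objective and for the predictor work.

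The effect is probably small. The range of 2 to 10 prospective patients rests on an assumed 1% to 5% frequency and on the protocol's rough estimate of 100 patients per year. Any statement about the share of true positives missed needs a further assumption on prevalence and should not be read as a finding. The primary endpoint does not use this item. The case for changing it is that the correction costs almost nothing now and much more once data have been collected.

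**What to change.** In the list of clinical data, delete the restriction to events older than 6 months. Collect any infarction, coronary insufficiency or stroke before RDN, with the date of the latest event. Report the item in three categories: none, 6 months or less, and more than 6 months before RDN.

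State that the interval is counted back from the date of the procedure and not from the date of inclusion, so that events after RDN in retrospective patients cannot enter as baseline history.

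The cost is one changed eCRF item and one added date field, both filled from the medical record already used as the source. The category above 6 months preserves what the present item would have given for events before RDN, so nothing in the baseline description is lost.
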